Postpartum women are at particularly high risk of unintended pregnancy.³ While some women have access to contraception in the hospital after delivery, provision varies and typically women do not receive contraception until the 6-week postpartum visit. Unfortunately, the timing of the 6-week visit is not based on current evidence about women's sexual activity after pregnancy or the need for timely PP contraception; thus, over half of women are at risk for a rapid repeat pregnancy.³⁰ Glazer and colleagues found 29% of women were using no contraceptive method at 4-6 months postpartum despite the fact they had resumed sexual intercourse and 32% percent of the study population were relying on less effective methods.³⁰

In contrast to the PP visit, the Well-Baby Visit (WBV) is highly utilized. In 2011-2012, 90.9% of U.S. infants received visits during the first year of life.¹⁴ Because women are more likely to obtain care for their infants, compared to their own PP care, they are likely to attend multiple visits in the pediatric setting during the PP period. In addition, the WBV is increasingly acknowledged as a site of care where maternal health issues can be addressed. AAP Bright Futures guidelines for health supervision encourage providers to assess maternal well-being as part of routine care of infants.³¹ This approach is particularly salient for the many women who do not attend a routine PP visit or who do not select a method of contraception during their PP visit. While a similar model may exist for women who seek care from a family physician who can provide care to both the mother and her infant, for most families, adult care is separate from pediatric care. Family physicians provide 17% of primary care visits for children ages 0-4, while pediatricians provide the remainder.³²

To both improve the delivery of interconception care to women of reproductive age and to facilitate discussion of contraceptive needs as part of this care, the Centers for Disease Control and Prevention (CDC) recommends use of a **Reproductive Life Plan Tool**.¹⁰ To date, literature on RLPTs has mostly focused on their use in women-focused primary care settings or in family planning settings.^{16,17,19-21,33} This study seeks to test the use of a streamlined self-administered RLPT (attachment) with all PP women attending a 2-month WBV with their infant. Pediatricians will then use the RLPT to

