assess women's need for well-woman primary care, then refer and provide an appointment for care for women who desire one.

Specific Aims

Aim I. To determine if introducing a self-administered Reproductive Life Planning Tool (RLPT) with postpartum mothers during the 2-month WBV will increase the proportion of women receiving a well-woman primary care health visit by 6 months postpartum.

Aim Ia. To determine if introducing a self-administered Reproductive Life Planning Tool (RLPT) with postpartum mothers during the 2-month WBV will increase utilization rates of contraception by 6 months postpartum.

Aim II: To assess the extent of system adoption as well as patient-, provider-, and systems-level barriers and facilitators to integrating a self-administered Reproductive Life Planning Tool designed to facilitate referral of postpartum women for primary well-woman care within the context of a pediatric clinic.

Study Design and Intervention

This is a single-site system-level pilot study to measure the impact of a self-administered RLPT (attachment) during the 2-month WBV on PP women's subsequent receipt of primary health care and contraception, compared to usual care. To facilitate women's uptake of a referral for well-woman primary care, women will be offered the opportunity to schedule a visit for herself on the same day as her infant's next WBV or the first available visit if she needs more immediate care. This study will have two phases: **phase 1** is enrollment of a control or baseline group, followed by a washout period; **phase 2** is enrollment of the intervention group (intervention).

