All survey data will be directly entered into REDcap web-based data capture screens that will be programmed and tested prior to the study. Data will be imported to SAS for analysis. Variables (Table 1) will be merged across time point by study ID and cleaned and recoded. Focus groups will be recorded, transcribed, and uploaded to DeDoose qualitative analysis software. Completion of the Grey Box (physician section of the tool) will be a measure of provider “adoption” of the intervention; completion rates will be tracked by comparing completed forms with completed clinic visits for 2-month WBVs. Completed clinic visit data are available in our existing medical record scheduling system.

Analysis

Specific Aim I and Ia: Baseline characteristics will be assessed for equivalency across groups using chi-square tests for categorical and t-tests for continuous variables. Unbalanced characteristics will be adjusted for in further analyses. The primary outcome, receipt of primary care services for women by 6 months PP (SA I) will be ascertained both by self-report during the 6-month phone interview and by medical record review, in order to minimize missing data. Evidence of a visit from either source

will be counted as receipt. Utilization, type and duration of contraception (SA 1a) by 6 months PP will be assessed similarly. An intent-to-treat analysis will be performed for SA I and 1a. A crude relative risk (RR) and risk difference (RD) will be calculated with 95% confidence intervals to estimate the effect of the intervention on primary outcomes. If adjustment is needed for covariates, RRs and RDs will be estimated using the average marginal predictions from a fitted logistic regression model with the following form:⁴¹

$$\text{logit}(y) = \beta_0 + \beta_1x_1 + \beta_2x_2 + \dots + \beta_kx_k, \text{ where:}$$

y =	SA 1: Woman's primary care visit by 6 months (1 = Yes/0 = No)
	SA 1a: Use of contraception at 6 months (1 = Yes/0 = No)
x ₁ =	RLPT Intervention (1 = Intervention/0 = Control)
x ₂ – x _k =	Unbalanced covariates

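### Contraception is measured by 6 months in the aim but at 6 months in the model, and its only coding rule, borrowed from visits, does not suit a state that can stop

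*Combined protocol and SAP*

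**What the plan says.** Three places in the combined protocol and SAP define the contraception outcome.

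- Specific Aims, Aim Ia: the tool "will increase utilization rates of contraception by 6 months postpartum".
- Analysis, Specific Aim I and Ia, ascertainment text: "Utilization, type and duration of contraception (SA 1a) by 6 months PP will be assessed similarly". The comparison is with the primary outcome, a primary care visit, which "will be ascertained both by self-report during the 6-month phone interview and by medical record review, in order to minimize missing data". For that outcome, "Evidence of a visit from either source" is enough to code the visit as received.
- Analysis, Specific Aim I and Ia, model definition: "SA 1a: Use of contraception at 6 months (1 = Yes/0 = No". The line above it keeps the cumulative wording for the other outcome: "SA 1: Woman's primary care visit by 6 months (1 = Yes/0 = No".

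Table 1 lists use, duration and method of contraception, collected at 6 months postpartum from phone survey and chart review, without saying whether past or current use is meant. Data Sources and Collection lists use and type among the interview topics, allows the call to take place as late as 9 months postpartum, and sets chart review at baseline and 6 months.

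**The concern.** Use by a date and use at a date are different outcomes when use can stop. A woman who started a method at 6 weeks and gave it up at 4 months is a user under the first and a non-user under the second. The same data would give two different risk differences and relative risks, and the plan does not say which is reported.

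The ascertainment rule adds to this. A yes-if-either rule is right for a visit, because a positive record in one source cannot be undone by the other. For a current state, an older positive record and a later negative report can both be true, and the rule would code that woman as a user. Use that began before the 2-month visit would count too, although the intervention could not have caused it. Without an agreed definition, two analysts could code the outcome of a named aim differently and both claim to follow the plan.

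**Working it through.** The plan states no contraception rate, discontinuation rate or target effect, so there is no figure of its own to reproduce. The check compares the texts and then illustrates the consequence on assumed rates.

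**Texts side by side**

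| Place | Time frame | Coding rule |
|---|---|---|
| Aim Ia | by 6 months | none |
| Ascertainment text | by 6 months | similar to the visit outcome |
| Model | at 6 months, yes/no | none |
| Table 1 | collected at 6 months | none; both sources listed |

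No text says which source prevails when they disagree, how a woman who started and stopped is coded, or how duration enters the yes/no outcome.

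**Formula.** Let p be the proportion currently using a method at 6 months, and f the share of current non-users with evidence of earlier use in either source. Under a direct reading of the either-source rule, the coded rate is p + (1 − p)f. With f equal in both arms, the coded risk difference is (p₁ − p₀)(1 − f).

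**Illustration 1, equal f.** Assumed control rate: 71%, that is 100% − 29%, from the Background figure that "29% of women were using no contraceptive method at 4-6 months postpartum". That figure comes from a cited study and concerns women who had resumed intercourse, so it is only a rough anchor. Assumed intervention rate: 81%.

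| f | Control | Intervention | Risk difference |
|---|---|---|---|
| 0 | 71.0% | 81.0% | 10 points |
| 30% | 0.71 + 0.29 × 0.3 = 79.7% | 0.81 + 0.19 × 0.3 = 86.7% | 7 points |
| 50% | 0.71 + 0.29 × 0.5 = 85.5% | 0.81 + 0.19 × 0.5 = 90.5% | 5 points |
| 70% | 0.71 + 0.29 × 0.7 = 91.3% | 0.81 + 0.19 × 0.7 = 94.3% | 3 points |

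With other assumed rates, 60% against 75%, the 15-point difference becomes 13.5, 11.3 and 7.5 points at f = 10%, 25% and 50%.

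**Illustration 2, unequal f and no true difference.** Assume current use of 60% in both arms.

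- f = 10% in controls and 25% in the intervention arm: 0.60 + 0.40 × 0.10 = 64% against 0.60 + 0.40 × 0.25 = 70%, a spurious 6 points.
- f = 10% and 40%: 64% against 0.60 + 0.40 × 0.40 = 76%, a spurious 12 points.

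Unequal f is plausible. The intervention refers women to a clinic within the same health system, and the plan says that it cannot confirm visits outside that system, so chart evidence may build up faster in the intervention arm.

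**Scale against precision.** With 50 women per arm and 71% against 81%, the 95% half-width for the risk difference is 1.96 × √(0.71 × 0.29/50 + 0.81 × 0.19/50) = 0.166, about 17 points.

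**The case against.** The best defence is that the reference to similar assessment means only that both sources are consulted. The either-source sentence is about visits. The sentence after it covers utilization, type and duration together, and type and duration cannot be scored by a yes-if-either rule. The model line is the only place that defines the yes/no outcome, and it says at 6 months, directly below a line that keeps by 6 months for visits. Duration is to be collected, so women who stopped may be identifiable.

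Much of this stands. A reader might infer that the plan adopts ever-use as its outcome, or that it lets an early prescription in the chart overrule the woman's own report. The documents do not go that far: they never use the term ever-use, never say that a prescription counts as use, and never rank the chart above the interview. But the defence does not remove the problem. If only the sources carry over, the plan has no rule for disagreement between them. Duration is not used anywhere to define the outcome, and the aim still says by 6 months.

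It is also fair that contraception is a sub-aim, that the sample size is justified by primary care receipt, and that shifts of 3 to 7 points lie well inside a half-width of about 17. That limits the damage in this pilot. It does not make the outcome codable.

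**Conclusion.** The conflict is in the current text: the aim and ascertainment sentence use one time frame, the model another. The one coding rule on offer, read directly, does not deliver the outcome that the model names. This should be corrected before the data are coded.

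The size cannot be derived from the documents. The fall from 10 points to 7, 5 or 3 rests on assumed rates and on an equal share of stopped users in both arms. A reader might conclude that the rule necessarily hides an intervention effect. That is not supported: with unequal shares and equal current use, a spurious difference of 6 to 12 points appears in the illustration. The direction is uncertain.

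**What to change.** - Use one definition, current method use at 6 months postpartum, in Aim Ia, Table 1, the ascertainment text and the model.
- Limit the either-source rule to visits.
- For contraception, let the interview answer decide when the sources disagree. Anchor the question to the 6-month date, because a call at up to 9 months would otherwise record use at the time of the call.
- When the interview is missing, use the chart only for a method documented as in effect at 6 months. Otherwise code the outcome as missing, not as non-use.
- Report any use after the index well-baby visit as a secondary outcome.

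The cost is wording in four places, one coding rule and possibly one dated interview item; the survey itself is not in the documents, so whether it already asks this cannot be checked. The downside is slightly more missing outcome data among women not reached by phone, which works somewhat against the plan's stated reason for using two sources.

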Though this is a system-level intervention, the intervention is targeting only the 2-month WBV, thus we do not expect a RLPT will be offered to a woman more than once. After consent is obtained, the RA will cross-check the participant list using a secure network on a tablet device to ensure that the woman is not already enrolled. Each RLPT will be linked to the infant by medical record number and date of birth. Limited physician characteristics (male/female, trainee/faculty) will be recorded; no physician names will be collected. The RLPTs for women who are consented and enrolled in the study will remain intact and all data will be collected from the tool and linked to the enrolled mother. The RLPTs for women who are *not* enrolled into the study will be de-identified after the Edinburgh tool is scanned by removing and shredding the patient sticker so no identifying information remains on the form. This will allow us to calculate clinic-specific adoption rates and examine the extent to which provider and system characteristics, such as the type of physician (e.g., attending versus resident), demographic characteristics of the physician (e.g., sex), and clinic operational factors (e.g., morning versus afternoon clinic; day of the week), influences adoption of the intervention (Table 1).

Consent for Intervention Group: Informed consent will be obtained for: 1) a baseline survey; 2) a phone survey at 6 months PP; and 3) access to a woman's medical records to document receipt of health care services. Women will be reimbursed for their time with gift cards [\$10 at baseline and \$10 at 6 months]. The RA will log the recruitment process, including number of women approached and if women accepted or refused, participation.

Pediatrician Training: Pediatricians (faculty and resident physicians) will all receive a 1-hour formal training on using the RLPT prior to the start of the study, offered at three different times to accommodate physician schedules. Research staff will touch-base

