with pediatricians weekly during the first 4 weeks of the study, and monthly thereafter, to answer questions and encourage consistent provider use of the tool. We will schedule a ‘refresher’ training 3 months after the start of the study to reinforce appropriate use of the tool. During the training, physicians will be instructed on how to start a conversation with women, what to document on the tool, and how to initiate a referral if needed. Physicians are *not* expected to provide contraceptive counseling to mothers, only to engage women in a discussion about their health care needs. An information sheet about the study will be given to all pediatric providers who are trained.

Selection of control group: The control group will be enrolled during phase 1 (first 4 months) prior to the introduction of the intervention. Similar to the intervention group, women will be recruited by an RA before, during or after the health care visit and screened for eligibility. Informed consent will be obtained for a baseline survey using the same procedure as described for the intervention group (same gift card amounts). Because we are studying health behaviors, we cannot share the specific aims of the study with control group participants as this could bias behavior. The control group participants will be told that this is a study monitoring women’s general health care experiences at UIH. After enrollment of the control group, a 6-week washout period prior to phase 2 (intervention) will ensure women are not enrolled into both arms of the study.

Sample: This pilot study will enroll at least 50 women per group. This sample size will provide a stable estimate of the intervention’s effect on primary care receipt by 6 months postpartum for power calculations for a larger, subsequent study of intervention effectiveness. There are approximately 200 deliveries per month at UIH, with 57% (114) of these infants having a 2-month WBV at UIH. For the 4-month period of recruitment each for control and intervention groups, we can meet our target enrollment of 50 in each group by recruiting women during four of the ten half-day CYC clinics per week, assuming a conservative participation rate of 40%.

Table 1 Study Variable Table

Variable	Specific Aim	Level of Measurement	Time of Collection	Tool	Variable Type
Demographic Data	I	Women	Enrollment	Baseline survey	Covariate
Physician Characteristics Male/Female, Trainee/Faculty	II	Physicians	Enrollment	Medical record schedule	Covariate

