Specific Aim II: Patient and physician facilitators, barriers and satisfaction data will be gathered from the RLPT, surveys, and focus groups. System adoption will be defined as the number of completed RLPT forms clinic-wide during the intervention (for enrollees and non-enrollees) divided by the total number of eligible visits during that time period, which will be ascertained through the clinic's scheduling database. Adoption will be compared across provider (e.g., status) and clinic operation factors (e.g., day of week) using chi-square tests. Adoption statistics will be shared with providers prior to focus groups, allowing them to elaborate on these findings. Qualitative focus group data from providers will be coded according to domains and analyzed for emergent themes related to feasibility and acceptability. Women's perceptions of feasibility and acceptability will be derived through the survey data and will be analyzed by other key covariates.

Although the findings of this study will reflect the experiences of low-income women at one large medical center in Chicago, they are likely to be relevant to the experiences of many low-income women. While a hospital outpatient clinic is a unique health care setting, the experience of having a pediatrician discuss new mothers' health needs and refer them for their own care is likely to be similar across pediatric practices. This study will add to the emerging literature related to a dual care focus for mother and infant. If this intervention is successful, it will provide evidence of the feasibility of introducing a system-level intervention related to women's health into pediatric practice. This information can inform changes in payment and policy to support the ability of pediatricians to discuss women's health needs and facilitate referral with mothers at their infants' WBV, with the ultimate goal of increasing women's use of primary care and PP contraception, preventing rapid repeat and unintended pregnancies, and ultimately decreasing adverse pregnancy outcomes.

References

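### Aim II tests adoption by physician status and sex with visit-level chi-square tests and lists no physician code, so these p-values are too small if physicians differ in adoption

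*Combined protocol and SAP*

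**What the plan says.** The Analysis section for Specific Aim II defines system adoption as completed forms across the whole clinic, "divided by the total number of eligible visits during that time period". It then states: "Adoption will be compared across provider (e.g., status) and clinic operation factors (e.g., day of week) using chi-square tests". No other method is named for these comparisons.

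The recruitment section gives the provider factors as attending or resident status and physician sex. On what is kept about physicians it says: "Limited physician characteristics (male/female, trainee/faculty) will be recorded; no physician names will be collected". Table 1 has a row for these two characteristics and a row for visit time and weekday, both taken from the medical record schedule. It has no row for a physician identifier.

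Data Management adds a measure that belongs to the physician: "Completion of the Grey Box (physician section of the tool) will be a measure of provider" adoption. Table 1 also lists Grey Box completion under adoption. On the denominator, Data Management says: "Completed clinic visit data are available in our existing medical record scheduling system".

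Forms of women who do not enrol are de-identified "by removing and shredding the patient sticker so no identifying information remains on the form". Adoption results go to the providers before the focus groups.

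**The concern.** A Pearson chi-square test on visits treats each visit as an independent observation. Status and sex do not vary within a physician, so all of one physician's visits fall on the same side of each comparison. If some physicians habitually complete the form and others do not, the real information lies closer to the number of physicians than to the number of visits. The unadjusted variance is then too small, and so on average is the p-value.

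This matters most for the Grey Box, which is the physician's own act. The mother's section may cluster little. The Pediatrician Training section plans regular contact "to answer questions and encourage consistent provider use of the tool", which makes differences between physicians plausible but does not show them.

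At stake is a chance difference among a few physicians being read as a trainee/faculty or sex effect, and then shaping the focus-group discussion.

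**Working it through.** **The plan's own figure.** The Sample section gives about 200 deliveries a month, "with 57% (114) of these infants having a 2-month WBV at UIH". 200 × 0.57 = 114, which reproduces. Over the 4-month recruitment period, 114 × 4 = 456 visits. Using 456 assumes that the adoption window equals the recruitment window.

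**Assumed inputs, not in the documents.** Number of physicians k: 20, 40 or 60. ICC of adoption within physician: 0.02 to 0.2. Half the physicians in each group, even caseloads, no true difference between groups.

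**Formulas.** With n visits, the design effect for a factor fixed within physician is DEFF = 1 + (n/k − 1) × ICC. The true size of a nominal 5% test is 2 × [1 − Φ(1.96/√DEFF)].

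- k = 60, ICC 0.02: 456/60 = 7.6; DEFF = 1 + 6.6 × 0.02 = 1.13; size 6.5%.
- k = 40, ICC 0.05: 456/40 = 11.4; DEFF = 1 + 10.4 × 0.05 = 1.52; size 11.2%.
- k = 20, ICC 0.2: 456/20 = 22.8; DEFF = 1 + 21.8 × 0.2 = 5.36; size 39.7%.

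Full grid of true size at n = 456:

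| Physicians | ICC 0.02 | ICC 0.05 | ICC 0.1 | ICC 0.2 |
|---|---|---|---|---|
| 20 | 10.2% | 17.5% | 27.2% | 39.7% |
| 40 | 7.5% | 11.2% | 17.0% | 26.4% |
| 60 | 6.5% | 8.9% | 12.8% | 19.8% |

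**Check by simulation.** A beta-binomial simulation with 20,000 replicates per cell and 70% adoption agrees with every cell to within about half a percentage point. At ICC = 0 it returns 5%, so the problem exists only if physicians differ. Assumed adoption of 50% or 90% changes little.

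**Sensitivity, for the three worked cases in order.**
- Half as many visits (228), simulated: 5.8%, 7.9% and 26.8%.
- Uneven caseloads at 456 visits, two assumed patterns: 7.4% to 8.6%, 15% to 18%, and 47% to 51%.

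**Effect on precision.** At an assumed 70% adoption and 228 visits per group, the 95% CI half-width for a status difference is 1.96 × √(2 × 0.7 × 0.3/228 × DEFF). That is 8.4 points with no clustering, and 9.0, 10.4 and 19.5 points in the three cases.

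**Check of the remedy.** Assume 50 residents with 5 visits each and 10 faculty with 20 each (450 visits), 70% adoption and ICC 0 to 0.2. An equal-variance t-test on physician-level proportions then has a true size of only 0.3% to 2.5%. Welch's unequal-variance test gives about 5% to 6%.

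**The case against.** The strongest reply is that the size rests wholly on assumption. Physician numbers, ICC, caseloads and adoption are not in the documents, and the range starts at a near-harmless 6.5%. Shared training, regular contact and a refresher should narrow differences between physicians. This stands: the upper end is not a forecast for this clinic.

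It is also fair that Aim II is a secondary aim of a single-site pilot, that no alpha, power or decision rule attaches to these tests, and that providers can question the results shown to them. This limits the weight of the point but does not make the p-values correct.

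Three stronger readings are tempting, and the documents do not support them.

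- A reader might take 456 as an upper limit on visits. It is only an assumed count. It starts from UIH deliveries, so infants born elsewhere are left out. Adoption is counted over the intervention, whose length is not stated to be 4 months. Absent or ineligible mothers would lower it.
- A reader might infer that the plan has no source for physician type, weekday or session. Table 1 names the medical record schedule. That system may also hold provider identity, and excluding names does not exclude a code. What is missing is a listed physician code and a stated use for it.
- A reader might extend the claim to weekday. The direction there depends on schedules that are not given. With 40 physicians and ICC 0.02 to 0.2, simulated error falls from 4.5% to 2.3% if each physician's visits spread over all days, but rises from 10% to 56% if each works one fixed day.

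**Conclusion.** The point holds for the status and sex comparisons, and most clearly for Grey Box completion. As written, the analysis gives p-values that are too small whenever physicians differ in adoption. Over the assumed range, with even caseloads, the true error of a nominal 5% test is about 6.5% to 40%, and about 11% in a middle case (40 physicians, ICC 0.05). Uneven caseloads raise these figures and fewer visits lower them.

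The documents do not show that physicians differ, so it cannot be said that the planned tests will mislead. The pooled adoption rate is not biased by this, and Aim I is untouched. The point is minor, but it is best settled before data collection: once a non-enrollee's sticker is shredded, tying that form to a physician may no longer be possible.

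**What to change.** Before the sticker is removed, write a non-name physician study code on each form. Attach the same code to the visit counts from the scheduling database, so that adoption can be expressed as forms out of visits for each physician.

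Test status and sex on Grey Box completion, reported separately from the mother's section. Either compare physician-level proportions with a Welch test, or use a GEE, mixed model or Rao-Scott test clustered on physician with a small-sample correction. Give cluster-robust 95% CIs. An equal-variance t-test should be avoided, since residents and faculty may carry different caseloads.

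If no code can be recorded, report the status and sex contrasts descriptively, without p-values. This is the cheapest adequate option.

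The cost is one coded field per form, a different SAS procedure and wider intervals. Ethics wording must cover the forms of women who decline, because the recruitment section says they take no part in research data collection. The code list must be held securely, since its holder could re-identify physicians.

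One limitation should be stated. Residents work under supervising faculty, and a single physician code does not capture clustering by supervisor. With 40 physicians, physician ICC 0.05 and supervisor ICC 0.02 to 0.05 on resident visits (all assumed), the physician-level test had a simulated error of 5.8% to 6.8% with 10 supervisors and 7.4% to 10.8% with 5.
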